5.5.4.3 Rescue Medication Use

Blinded Phase:

The number of days that rescue medication (RM) was taken since the previous visit will be collected throughout the trial at scheduled visits and safety telephone calls.

To standardize between patients, the total number of days RM was taken will be calculated as the sum of all reported records within a period. Hence, the average number of days RM was taken per 28 days within a period will be calculated as follows:

$(\text{Total number of days RM was taken during the period} \div \text{Number of days in the period}) \times 28$

This will be calculated for both the baseline period and treatment period. The number of days in a period will be calculated as the number of days from the visit prior to the first recorded value in the period to the day of the last recorded value in the period. The baseline period refers to the period between Visit 2 and Visit 3. The treatment period refers to the period between Visit 3 and Visit 10.

The number of days RM was taken per 28 days will be summarized by period and treatment arm. The change from the baseline period will also be included.

The change from the baseline period to the treatment period will be analyzed using an ANCOVA approach. The model will include the baseline period and stratified age group as covariates and treatment arm as fixed factor.

The estimated least squares means, treatment difference, together with the 95% CIs and p-value will be presented.

Open-label Extension:

Descriptive summaries described above for the blinded phase will be repeated for the OLE period. The OLE period refers to the period between Visit B1 and the last available visit in the OLE phase.

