5. STATISTICAL METHODS

5.1 General Considerations

In all tables, listings and figures for the double-blind phase, the trial medications will be referred to and labelled as per Table 1.

Table 1 Blinded Phase Trial Treatments

Endpoint	Actual Treatment	Treatment Label
Efficacy	Pooled Placebo	Placebo
Safety	25 mg/kg/day Placebo	Placebo 25 mg/kg
	50 mg/kg/day Placebo	Placebo 50 mg/kg
All	25 mg/kg/day GWP42003-P	25 mg/kg
All	50 mg/kg/day GWP42003-P	50 mg/kg

For safety tables where placebo is split by dosing volume, an additional Pooled Placebo column will be included.

For OLE tables, columns will be included for treatment received during the double-blind phase (GWP42003-P or placebo, i.e. not split by dose) and overall.

In all tables, listings and figures, the trial visits will be referred to and labelled as per Table 2.

Table 2 Trial Visits

Actual Visit	Visit Label
Visit 1: Screening	Day -35
Visit 2: Day -28, baseline visit	Day -28
Visit 3: Day 1, Randomization	Day 1
Visit 4: Day 15	Day 15
Visit 5: Day 29	Day 29
Visit 6: Day 43	Day 43
Visit 7: Day 57	Day 57
Visit 8: Day 71, Telephone	Day 71
Visit 9: Day 85	Day 85
Visit 10: Day 113	End of Treatment
Visit 11: Day 123	End of Taper
Visit 12: Day 151	Safety Follow-Up
Visit B1: Day 1, Enrollment	OLE Day 1
Visit B2: Day 15	OLE Day 15
Visit B3: Day 36	OLE Day 36
Visit B4: Day 92	OLE Day 92
Visit B5: Day 141, Re-stocking of supplies	OLE Day 141
Visit B6: Day 183	OLE Day 183
Visit B7: Day 232, Re-stocking of supplies	OLE Day 232
Visit B8: Day 274	OLE Day 274
Visit B9: Day 323, Re-stocking of supplies	OLE Day 323
Visit B10: Day 365	OLE End of Treatment
Visit B11: Day 375	OLE End of Taper
Visit B12: Day 389	OLE Post-taper Safety Telephone Call
Day 403	OLE Follow-Up

Unless stated otherwise, continuous variables will be summarized showing the number of non-missing values (n), mean, standard deviation, median, minimum and maximum and categorical variables will be summarized showing the number and percentage of patients falling in each category. For continuous summaries of seizure frequency, the lower and upper quartiles will also be presented.

Minimum and maximum values will be presented to the same decimal precision as the raw data. Mean and median will be presented to one more decimal place than the raw data, and standard deviation to 2 more decimal places than the raw data. Percentages will be presented to one decimal place.

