Where X corresponds to the treatment period estimate, or GWP42003-P ratio, and Y corresponds to the baseline period estimate, or placebo arm ratio.

Primary efficacy analysis will be performed using the ITT analysis set.

TSC-associated seizure frequency (28-day average) and percentage change in seizure frequency will also be presented using summary statistics. Percentage change from baseline in TSC-associated seizure frequency will be calculated as:

$$((\text{Frequency during the treatment period} - \text{Frequency during baseline}) \div \text{Frequency during baseline}) \times 100$$

The frequency during each period will be based on 28 day averages and calculated as:

$$(\text{Number of seizures in the period} \div \text{Number of reported days in IVRS in the period}) \times 28$$

For the TSC-associated seizure endpoints only, if patients are randomized with no TSC-associated seizures during the baseline period then the percentage change from baseline will be calculated as:

$$(\text{Frequency during the treatment period} + 1) \times 100$$

Open-label Extension:

The primary endpoint for the OLE is the safety of GWP42003-P, evaluated by assessing the incidence, type and severity of AEs. Data will be presented as per Section 5.6.2.

However, percentage change from baseline in TSC-associated seizure frequency is considered a key secondary endpoint for the OLE.

In the OLE, seizures are recorded on a weekly basis rather than daily. Caregivers/patients are expected to call the IVRS system to record the number of seizure subtypes experienced every 7 days during the OLE. TSC-associated seizure frequency per 28 days will be calculated for each of the periods described in Section 5.5.1. All calls that take place during the period in question will contribute to the calculation of the average number of seizures per day in that period only.

The average number of seizures per day in the period will be calculated as the average of:

$$\text{Number of seizures reported} \div \text{Number of days since last IVRS call}$$

The number of days since the last call will be calculated as follows, and is dependent on whether the call took place <7, 7 or >7 days after the previous call (or after the date of OLE Day 1 in the case of the first call in the first period):

- If the call takes place exactly 7 days after the previous call, then the number of days since the last call will be 7.

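### Rescue-medication rate: a blank record between two recorded values counts as zero use, and the open-label window is not clearly limited to time on treatment

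*SAP*

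**What the plan says.** Section 5.5.4.3 of the SAP describes what each record covers: "The number of days that rescue medication (RM) was taken since the previous visit will be collected throughout the trial at scheduled visits and safety" (the last words refer to safety calls). For the numerator, "the total number of days RM was taken will be calculated as the sum of all reported records within a period". The denominator is a count of this kind: "number of days from the visit prior to the first recorded value in the period to the day of the last recorded value in the", meaning whichever window is being summarised. The ratio is multiplied by 28.

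The windows differ by phase. Baseline runs from Visit 2 to Visit 3. In the blinded phase, "The treatment period refers to the period between Visit 3 and Visit 10". In the extension, "The OLE period refers to the period between Visit B1 and the last available visit in the OLE phase".

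The blinded change from baseline is analysed by ANCOVA, with confidence intervals and a p-value. The extension is summarised descriptively.

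Three other places bear on the point:

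- Section 5.5.2 divides the blinded-phase seizure count by the "Number of reported days in IVRS in the period", so unreported days are left out of the denominator.
- Section 5.1.3.2 defines the last visit for clinic-visit endpoints and leaves out the end-of-taper and safety follow-up visits.
- Table 2 in Section 5.1 gives OLE labels to three contacts after OLE end of treatment (Day 365): end of taper (Day 375), the "OLE Post-taper Safety Telephone Call" (Day 389) and follow-up (Day 403). Section 3.1 counts the taper as part of the OLE.

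**The concern.** There are two separate weaknesses.

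The first is a mismatch between numerator and denominator. Each record looks back only to the previous visit. If a visit takes place but the rescue field is left blank, the next record does not reach back over the gap. The sum then lacks that interval while the span still includes it, so a missing value is handled as zero use. On the Table 2 schedule the baseline period is one interval and cannot contain such a gap. The error can therefore only lower the post-baseline rate, which makes the change from baseline look better than it was. In the blinded phase that change is formally tested.

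The second is the end of the open-label window. The blinded window stops at end of treatment. The open-label window uses a term that Section 5.1.3.2 does not define, and does not refer to that section. Since rescue use is collected throughout the trial, including at safety calls, a programmer could build a window that takes in the taper and the time off drug. The open-label rate would then not be purely a rate on treatment, and would not be on the same footing as the blinded one.

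**Working it through.** The SAP states no numerical result for this endpoint, so there is no figure to reproduce. The check is day-count arithmetic on the nominal days of Table 2.

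**Blinded phase.** Visits from Visit 3 to Visit 10 fall on Days 1, 15, 29, 43, 57, 71, 85 and 113, a span of 113 − 1 = 112 days. All intervals are 14 days except the last (Day 85 to Day 113), which is 28. Remove one record at a time, assuming that the visit itself took place:

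| Blank record at | Denominator under the rule | Days covered by records | Covered ÷ denominator |
|---|---|---|---|
| Day 15 (leading) | 113 − 15 = 98 | 98 | 1.000 |
| Day 29, 43, 57, 71 or 85 (interior) | 112 | 112 − 14 = 98 | 0.875 |
| Day 113 (trailing) | 85 − 1 = 84 | 84 | 1.000 |

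With even use, one interior blank makes the rate 1 − 98/112 = 12.5% too low. Two interior blanks give 84/112 = 0.75, or 25% too low. If the true treatment-period rate is r days per 28, one interior blank moves that patient's change from baseline by −0.125 × r.

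**Open-label phase.** On-treatment days for a one-year completer are 365 − 1 = 364. The share of the window after end of treatment depends on the last contact with a recorded value:

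| Window ends at | Days in window | Days after Day 365 | Share |
|---|---|---|---|
| Day 365, end of treatment | 364 | 0 | 0% |
| Day 375, end of taper | 374 | 10 | 2.7% |
| Day 389, post-taper call | 388 | 24 | 6.2% |
| Day 403, follow-up | 402 | 38 | 9.5% |

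Of the 38 days, 403 − 375 = 28 (28/402 = 7.0%) come after the end of taper.

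A share of time is not itself a bias. If use after treatment is m times the on-treatment rate, the computed rate to Day 403 is (364 + 38m)/402 times the on-treatment rate. As an assumed range, m = 0 gives 364/402 = 0.91 and m = 3 gives 478/402 = 1.19.

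For an early leaver, assume treatment stops at OLE Day 92 and is followed by the same 38 days of taper and follow-up. The share is then 38/(91 + 38) = 38/129 = 29.5%.

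**The case against.** The strongest defence of the denominator is that it already deals with most missing records. It starts at the visit before the first value and stops at the last value, so time after withdrawal adds nothing. If a visit is missed altogether, the next record counts back to the previous visit and may cover the gap. This stands, and it confines the problem to attended visits with a blank field between two recorded values. A reader might infer that the rate generally divides by days without a record; the rule does not do that.

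A reader might also infer that one missing 28-day interval costs 25%. It does not. The only 28-day blinded interval ends at Visit 10, and a blank there is trailing and drops out. Nor do the documents support a claim that the comparison between arms is biased in a particular direction, because they say nothing about how often values are blank or in which arm.

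On the windows, a reader might conclude that none of the rates is a rate on treatment. That is wrong for the blinded phase, whose window is fixed at Visit 10. For the extension, inclusion of taper and follow-up is the literal reading, not an express rule, and Section 5.1.3.2 points the other way. Ending at the last available visit also has a sensible purpose. Section 5.1.4 foresees interim reporting with a data cut, when patients still on drug have no end-of-treatment visit. That explains the wording but does not remove the ambiguity for patients who have stopped: Section 5.5.1 ties the open-label seizure summaries to the OLE treatment phase, and Section 5.5.4.3 has no such limit.

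Finally, the endpoint is exploratory (Section 3.3.3), outside the testing hierarchy in Table 3, and the open-label summary is descriptive. That limits the consequence, not the validity of the point.

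**Conclusion.** The point holds in a narrow form.

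In the blinded phase, each interior blank at an attended visit lowers that patient's treatment-period rate by 12.5% and shifts the analysed change toward apparent improvement. This assumes nominal visit days, even use over time, and rescue records only at the contacts listed in Table 2. Leading and trailing gaps do no harm. The effect on the ANCOVA cannot be sized, because the frequency of blanks is not given.

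In the extension, the end of the window is ambiguous. Read literally, the part after end of treatment can reach 9.5% of the window for a one-year completer with a value recorded at Day 403. It is 2.7% if the window ends at end of taper, and larger for early leavers.

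This is a clarification worth making, not a threat to any main conclusion of the trial.

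**What to change.** Make two changes in Section 5.5.4.3.

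1. Define the number of days in a period, for baseline, treatment and OLE alike, as the sum of the inter-visit intervals that have a recorded rescue-medication value. Numerator and denominator then cover the same days, in line with the reported-days rule for seizures in Section 5.5.2.
2. End the OLE rescue window at the OLE end-of-treatment or early end-of-treatment visit. For patients still on drug at a data cut, end it at the last available on-treatment visit. Exclude end of taper, the post-taper call and follow-up explicitly, with a reference to Section 5.1.3.2, so that the window matches the blinded one.

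The cost is about two sentences in the SAP and minor programming. No new data are needed.

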5.5.4.4 Status Epilepticus

The number of episodes of status epilepticus will be collected daily via IVRS for the blinded phase and weekly via IVRS for the open-label extension.

The number of patients with status epilepticus will be presented for the baseline, treatment and OLE periods.

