3.3.2 Secondary Efficacy Endpoints

Blinded Phase:

The following endpoints will be compared between treatment arms over the 16-week, double-blind treatment period (all changes relative to baseline):

Key:

1. Number of patients considered treatment responders defined as those with a $\geq 50\%$ reduction in TSC-associated seizure frequency (see Section 5.1.3.7).
2. Change in Caregiver Global Impression of Change (CGIC) or Subject Global Impression of Change (SGIC) score.
3. Change in total seizures.

Other:

Antiepileptic Efficacy Measures:

- Number of patients considered treatment responders defined as those with a $\geq 25\%$, $\geq 50\%$, $\geq 75\%$ or 100% reduction in TSC-associated seizure frequency.
- Number of patients experiencing a $> 25\%$ worsening, $- 25$ to $+ 25\%$ no change, $25-50\%$ improvement, $50-75\%$ improvement or $> 75\%$ improvement in TSC-associated seizure frequency.
- Change in number of TSC-associated seizure-free days.
- Change in number of 'other' seizures (absence, myoclonic, focal sensory and infantile/epileptic spasms).

Growth and Development (in patients less than 18 years old):

- Change in serum insulin-like growth factor-1 (IGF-1) levels.
- Change in Tanner Staging score (for patients aged 10–17 [inclusive]).

Quality of Life:

- Changes in the Quality of Life in Childhood Epilepsy (QOLCE; patients 2–18 years) or Quality of Life in Epilepsy (QOLIE-31-P; patients 19+ years) score.
- Change in Physician Global Impression of Change (PGIC) score.

Safety and Tolerability:

- AEs.
- Clinical laboratory parameters.
- 12-lead electrocardiogram (ECG).
- Physical examination parameters.
- Vital signs.
- Columbia-Suicide Severity Rating Scale (C-SSRS: 19+ years) or C-SSRS Children's (6–18 years) score, where applicable.
- Number of inpatient hospitalizations due to epilepsy.
- Abuse liability.
- Effects on menstruation cycles (in females).

Open Label Extension:

The following endpoints will be assessed relative to the pre-randomization baseline of the blinded phase:

Key:

- Percentage change in number of TSC-associated seizures (average per 28 days).
- Number of patients considered treatment responders defined as those with a $\geq 50\%$ reduction in TSC-associated seizure frequency.
- Change in CGIC or SGIC score.
- Change in total seizures.

Other:

Antiepileptic Efficacy Measures:

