3.3.3 Exploratory Endpoints (Double-blind and Open-label Extension)

Antiepileptic Efficacy Measures:

- Change in composite focal seizure score (frequency \times severity).
- Change in number of seizures by subtype.
- Change in use of rescue medication.
- Change in the number of episodes of status epilepticus (convulsive and non-convulsive).
- Changes in duration of seizure subtypes as assessed by the Subject Global Impression of Change in Seizure Duration (SGIC-SD) or the Caregiver Global Impression of Change in Seizure Duration (CGIC-SD).

TAND:

Cognitive and Behavioral Function:

- Changes in Vineland Adaptive Behavior Scales, Second Edition (Vineland-II).

- Changes in Wechsler Scales (pre-school, primary, children, adult).
- Changes in Achenbach Child Behavior Checklists (CBCL) and Adult Behavior Checklist (ABCL).

Autistic Features:

Change in Social Communication Questionnaire (SCQ) score.

PK (Double-blind only):

- The plasma concentrations will be summarized by time window for CBD and its major metabolites following single and multiple doses of GWP42003-P. Where data allows, the area under the plasma concentration curve (AUC_{0-t}) from time zero to the last measurable time-point will be calculated.
- Plasma concentrations of concomitant AEDs before and after treatment with GWP42003-P, where available.

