5.1.3 Definitions

5.1.3.1 Baseline

For clinic visit based endpoints, baseline is defined as the last record or measure collected prior to the first dose of IMP.

For IVRS based endpoints, baseline will include all available data from the day of Visit 2 to Day 1 of the blinded phase.

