5.6.4.5 Inpatient Hospitalizations due to Epilepsy

The number of inpatient epilepsy-related hospitalizations since the previous visit are recorded at every visit starting from Visit 2.

The number of patients with inpatient epilepsy-related hospitalizations will be presented by visit, including OLE visits.

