Table Number	Title	Analysis Set
Table 9.10.5.2	Negative Binomial Regression Analysis of Tonic Seizure Count During Baseline and Titration and Maintenance Periods	ITT Analysis Set
Table 9.10.5.3	Summary and Analysis of Tonic Seizure Treatment Responders and Tonic Seizure Freedom During the Treatment Period	ITT Analysis Set
Table 9.10.5.4	Summary and Analysis of Tonic Seizure Treatment Responders and Tonic Seizure Freedom During the Titration and Maintenance Periods	ITT Analysis Set
Table 9.10.6	Summary of Clonic Seizure Frequency	ITT Analysis Set
Table 9.10.7	Summary of Atonic Seizure Frequency	ITT Analysis Set
Table 9.10.8	Summary of Absence Seizure Frequency	ITT Analysis Set
Table 9.10.9	Summary of Myoclonic Seizure Frequency	ITT Analysis Set
Table 9.10.10	Summary of Partial Sensory Seizure Frequency	ITT Analysis Set
Table 9.10.11	Summary of Infantile or Epileptic Spasm Frequency	ITT Analysis Set
Table 9.11.1	Summary of Number of Days of Rescue Medication Use	ITT Analysis Set
Table 9.11.2	Analysis of Change from Baseline in the Number of Days of Rescue Medication Use	ITT Analysis Set
Table 9.12	Summary of Patients with Status Epilepticus	ITT Analysis Set
Table 9.13.1	Summary of Subject/Caregiver Global Impression of Change in Seizure Duration	ITT Analysis Set
Table 9.13.2	Analysis of Subject/Caregiver Global Impression of Change in Seizure Duration	ITT Analysis Set
Table 9.14.1.1	Summary of the Vineland-II Adaptive Behavior Subdomain, Domain and Composite Scores	ITT Analysis Set
Table 9.14.1.2	Summary of the Vineland-II Adaptive Behavior Subdomain, Domain and Composite Adaptive Levels	ITT Analysis Set
Table 9.14.1.3	Analysis of Change from Baseline in the Vineland-II Adaptive Behavior Domain and Composite Scores	ITT Analysis Set
Table 9.14.1.4	Analysis of the Vineland-II Adaptive Behavior Domain and Composite Adaptive Levels	ITT Analysis Set
Table 9.14.2.1	Summary of the Vineland-II Maladaptive Behavior Subdomain and Index Scores	ITT Analysis Set
Table 9.14.2.2	Summary of the Vineland-II Maladaptive Behavior Subdomain and Index Adaptive Levels	ITT Analysis Set
Table 9.14.2.3	Analysis of Change from Baseline in the Vineland-II Maladaptive Behavior Index Score	ITT Analysis Set
Table 9.14.2.4	Analysis of the Vineland-II Maladaptive Behavior Index Adaptive Level	ITT Analysis Set
Table 9.15.1	Summary of Wechsler Tests	ITT Analysis Set
Table 9.15.2	Analysis of Wechsler Tests	ITT Analysis Set

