2.3.3 Robustness to Withdrawn Patients

There were higher proportions of patients in each treatment arm that withdrew during the blinded phase treatment period when compared with placebo. In order to assess the robustness of the results, 2 analyses in the following sections are proposed.

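### Status epilepticus and epilepsy hospitalizations are endpoints defined as event counts, but the plan tabulates only patients with an event, over unequal windows and with no rate

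*SAP*

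**What the plan says.** **Status epilepticus.** SAP Section 3.3.3 lists as an exploratory endpoint "Change in the number of episodes of status epilepticus (convulsive and non-convulsive"). Section 5.5.4.4 has episode counts reported through the IVRS, each day in the blinded phase and each week in the OLE. The only summary it then plans is "The number of patients with status epilepticus will be presented for the baseline, treatment and OLE periods". The matching output, Table 9.12 in Appendix 6, is titled "Summary of Patients with Status Epilepticus". No episode total, rate, change or convulsive/non-convulsive split is specified.

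**Epilepsy hospitalizations.** Section 3.3.2 lists "Number of inpatient hospitalizations due to epilepsy" under safety and tolerability. Section 5.6.4.5 has the count since the previous visit recorded from Visit 2 onward, but plans this: "The number of patients with inpatient epilepsy-related hospitalizations will be presented by visit, including OLE visits". There is no total for the baseline, treatment or OLE period, and no denominator is stated.

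**Neighbouring endpoints.** Seizure counts use an offset for reported days and 28-day averages (Section 5.5.2). Seizure-free days (Section 5.5.3.2.2) and rescue-medication days (Section 5.5.4.3) are also scaled to 28 days. Section 5.8, which records changes to planned analyses, mentions neither substitution.

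**The concern.** A count of patients with at least one event answers a different question from a change in number of episodes. It ignores repeat episodes, and it grows with the length of the window even when the risk is constant. A reader who sets the three status epilepticus columns side by side would see a rise on treatment and a larger one in the OLE with no change in risk. The OLE has no concurrent control to expose the artefact.

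For hospitalizations, patients per visit cannot be added up. The sum gives neither the number of hospitalizations nor the number of patients hospitalized in a period, and the visit intervals differ in length.

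Unequal follow-up also enters the comparison between arms. Section 2.3.3 of the SAP addendum reports that "There were higher proportions of patients in each treatment arm that withdrew during the blinded phase treatment period when compared with placebo". An arm observed for less time has fewer days in which to record a first event. The addendum's withdrawal analyses cover seizure counts only.

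**Working it through.** The SAP gives no event rate for either endpoint, so there is no stated figure to reproduce. Event rates and withdrawal sizes below are assumptions, shown as ranges.

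**Windows.** Section 5.1.3.1 says "baseline will include all available data from the day of Visit 2 to Day 1 of the blinded phase": Day -28 to Day 1 is 28 days, or 29 if Day 1 is counted (there is no Day 0). Treatment is Day 1 to 113 (Section 5.1.3.4). The initial OLE lasts at most one year (Section 3.1), taken as 365 days. The ratios to baseline are 113/28 = 4.04 and 365/28 = 13.04.

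**Status epilepticus, unchanged risk.** Let p be the share of patients with an episode in 28 days.

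- Equal risk in all patients: P(T) = 1 - (1 - p)^(T/28). For p = 5%, 1 - 0.95^4.04 = 18.7% and 1 - 0.95^13.04 = 48.8%.
- Risk varying between patients (gamma, shape k): mean rate m = k[(1 - p)^(-1/k) - 1] per 28 days, and P(T) = 1 - [1 + (m/k)(T/28)]^(-k). For p = 5% and k = 0.1, m = 0.067, giving 12.3% and 20.4%. For k = 1, the results are 17.5% and 40.7%.

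| Baseline p | Treatment, equal risk | OLE, equal risk | Treatment, k = 0.1 | OLE, k = 0.1 |
|---|---|---|---|---|
| 2% | 7.8% | 23.2% | 6.2% | 12.8% |
| 5% | 18.7% | 48.8% | 12.3% | 20.4% |
| 10% | 34.6% | 74.7% | 19.3% | 27.6% |
| 15% | 48.1% | 88.0% | 24.9% | 32.9% |

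From baseline to treatment the apparent rise is 3.2- to 3.9-fold with equal risk. With k = 0.1 it is 1.7-fold (24.9/15) to 3.1-fold (6.2/2). With 29 baseline days, the 18.7% becomes 18.1%.

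**Status epilepticus, unequal withdrawal.** Take 5% per 28 days in every arm, no placebo withdrawal, and a share w of active patients leaving on day d. The active figure is (1 - w)(18.7%) + w[1 - 0.95^(d/28)].

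- w = 20%, d = 14: 15.5%, risk ratio 0.83.
- w = 10%, d = 42: 17.6%, risk ratio 0.94.

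Per 70 patients this is 10.8 to 12.3 with an episode, against 13.1 on placebo. At 10% per 28 days the risk ratios are again 0.83 to 0.94.

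**Hospitalizations by visit, unchanged risk of 5% per 28 days.** Intervals come from SAP Table 2.

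| Visit | Interval | Expected share of patients |
|---|---|---|
| Visit 2 | 7 days | 1.3% |
| Visit 3 (baseline) | 28 days | 5.0% |
| Visits 4 to 9 | 14 days each | 2.5% each |
| Visit 10 | 28 days | 5.0% |
| OLE visits to Day 365 | 14 to 56 days | 2.5% to 9.8% |

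**The same cases as rates.** Under equal risk, -ln(0.95) = 0.0513, so there are 5.1 episodes per 100 patients per 28 days in every period. With k = 0.1 the figure is 6.7 in every period. If withdrawal is unrelated to risk, it lowers expected episodes and patient-days (from 113 to between 93.2 and 105.9 per patient) in proportion, so the rate is unchanged.

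**The case against.** The strongest reply is that blinded-phase tables are by randomized arm, and placebo is shown over the same Day 1 to 113 window. The blinded objectives are comparisons with placebo, no test is planned for either endpoint, and neither is in the hierarchy of SAP Table 3. This stands. A reader might infer that the active arms would look worse than placebo because of window length; the documents do not support that. What remains is the within-arm change, which is how the endpoint is worded, and the OLE.

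A reader might also infer that hospitalizations would show the same false worsening. They would not in the blinded phase: no on-treatment interval is longer than the 28-day baseline interval. Only the longer OLE intervals could show a rise, of up to about twofold.

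Nor is it supported that early withdrawal makes active treatment look strongly protective. The size of the excess is not given, the addendum is post hoc, and under the assumptions above the effect is one to two patients per 70. For hospitalizations it depends on the unstated denominator.

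Repeat events are not lost from the record: Listings 8.2.5 and 14.8 and their OLE versions hold them, and events reported as adverse events enter the by-event tables. But listings do not summarize the endpoint.

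Finally, the OLE column could be read as the 12-week periods of Section 5.5.1. For p = 5%, 84 days gives 1 - 0.95^3 = 14.3% with equal risk and 10.4% with k = 0.1 (1 - [1 + 0.670 × 3]^(-0.1)). The artefact shrinks but remains.

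**Conclusion.** The mismatch between endpoint and summary is clear from the SAP's text and needs no assumption: two endpoints defined as event counts, and collected as such, are reported only as patients with an event.

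For status epilepticus, the planned table confounds the within-arm change with window length. At an assumed 5% per 28 days, an unchanged risk shows about 12% to 19% on treatment and 20% to 49% over a full-year OLE; the upper ends require equal risk in all patients, and the OLE figures require 365 days for everyone. The randomized comparison is affected only by unequal withdrawal, with a risk ratio of about 0.83 to 0.94 under an assumed 10% to 20% excess at Day 14 to 42.

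For hospitalizations, the fault is the missing count and period total, together with unequal visit intervals that make an unchanged risk look halved at Visits 4 to 9. Importance is low to moderate: both summaries are descriptive and no confirmatory conclusion depends on them.

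**What to change.** Keep the patient counts and add the following.

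- **Section 5.5.4.4, Table 9.12 and OLE Table 9.11:** total episodes, convulsive and non-convulsive separately; observed patient-days; and the rate per 28 reported IVRS days, by arm, for baseline, treatment and OLE. State whether the OLE is one period or split into 12-week periods.
- **Section 5.6.4.5, Table 14.7 and OLE Table 14.7:** total hospitalizations and the rate per 28 observed days for baseline (Visit 2 to 3), treatment (Visit 3 to 10) and OLE, reusing the rescue-medication formula of Section 5.5.4.3. State the denominator for the by-visit percentages.

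The episode and hospitalization counts are already collected. The SAP does not say whether the IVRS entry distinguishes the two kinds of status epilepticus, so that should be confirmed. The cost is SAP wording and extra table rows. If events are few the rates will be imprecise, so they should be read with the totals and patient-days beside them.
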